5.2.1 Dose Selection/Modification

5.2.1.1 Dose Selection (Preparation)

The chosen dose for IMI/REL in subjects with normal renal function is IMI/REL 500mg/250 mg administered IV as an FDC once every 6 hours (q6h). For subjects with renal insufficiency or whose creatinine clearance changes during treatment with study therapy, the dose must be adjusted based upon the degree of renal function impairment, as determined by the estimated or actual creatinine clearance. Subjects should be carefully monitored for renal function during IV treatment. Dose adjustments are included in [Table 13](#).

Table 13 Administration Dosage of IMI/REL According to Renal Function

Creatinine Clearance (mL/min)	IMI/REL ^a
≥ 90	500/250 mg q6h
< 90 to ≥ 60	400/200 mg q6h
< 60 to ≥ 30	300/150 mg q6h
< 30 to ≥ 15	200/100 mg q6h

^a IMI/REL is provided as a single vial in a fixed-dose combination; therefore, the dose for each component will be adjusted equally during preparation. For example, a subject who has a creatinine clearance of 50 mL/min should receive a 300/150 mg q6h dose of IMI/REL according to the table.

Creatinine clearance in mL/min may be calculated from serum creatinine concentration by the following equation:

$$\text{Creatinine clearance: (Males)} = \frac{(\text{weight in kg}) \times (140 \text{ minus age})}{(72) \times (\text{creatinine in mg/dL})}$$

Creatinine clearance: (Females) = 0.85 X the value obtained using the formula above.

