Clinical Response Assessment (including sepsis if applicable) ²⁰			X	X	X		
Microbiological Response Rating ²¹			X	X	X		

1. IV study therapy should be administered for a minimum of 5 full days. The total duration of IV study therapy should not exceed 14 days.
 
2. This sample should be drawn for planned analysis of the association between genetic variants in DNA and drug response. This sample will not be collected at the site if there is either a local law or regulation prohibiting collection, or if the IRB/IEC does not approve the collection of the sample for these purposes. If the sample is collected, leftover extracted DNA will be stored for future biomedical research if the subject signs the FBR consent. If the planned genetic analysis is not approved, but FBR is approved and consent is given, this sample will be collected for the purpose of FBR.
 
3. The details of subject's infection-site diagnoses (cIAI or cUTI) will be documented separately on the appropriate eCRF(s). Details should include the diagnosis and additional diagnostic details associated with the infection site (e.g., characterization of the complicated nature of the cIAI or cUTI).
 
4. The most recently collected creatinine clearance should be used to support dosage determination. (refer to Table 13 in Section 5.2.1.1). Any local or central laboratory abnormalities in serum creatinine that result in an adverse event or a dose adjustment should be recorded.
 
5. APACHE II score is calculated at screening only for subjects with cIAI. Please refer to Appendix 12.4 for the parameters and instructions for calculation of APACHE II score.
 
6. Vital signs should be performed and documented on the appropriate electronic case report forms (eCRFs) at the Day 1 prior to administration of the first dose of study therapy and daily during IV study therapy. Vital signs should also be performed and documented at the additional visits specified.
 
7. For all subject, weight must be measured at baseline. Enter weight if a clinically significant weight change occurred and resulted in a change in CrCl category.
 
8. Monitor for adverse events and local infusion tolerability and collect infection-specific clinical signs and symptoms daily during IV study therapy and adverse experiences for 14 days after completion of IV study therapy. Laboratory abnormalities that emerge during IV therapy and are considered adverse experiences by the investigator must be followed until resolved or stabilized. Serious adverse experiences that are considered by the investigator to be related to the investigational product that is brought to the attention of the investigator at any time outside of 14 days post-therapy also must be reported immediately to the Sponsor.
 
9. Clinical signs and symptoms, radiographic (daily reporting not required for radiographic findings) and laboratory characteristics associated with the primary bacterial infection and with sepsis (see Table 14 in section 7.1.2.6) will be reviewed and documented on the appropriate electronic case report forms (eCRFs) daily during IV study therapy and at the additional visits specified.
 
10. Includes information regarding infection source control should be documented on the appropriate eCRF. Source control includes the following for each infection site: cUTI - baseline information associated with catheterization (e.g., recent surgery or instrumentation, presence of catheter/stent) as well as any details related to removal and/or replacement of urinary catheters at any time during the study. cIAI: details associated with the qualifying abdominal surgical intervention or any subsequent interventions, including an anonymized narrative of the operative note and/or interventional radiology report.
 
11. Blood for laboratory safety tests (hematology and chemistry) should be collected for submission to the central safety laboratory at Day 1 prior to administration of the first dose of study therapy, on Day 3 (OTX), and every 3 days thereafter until EOT (including the EOT visit). Blood should also be collected at TOC and FU. Urine for urinalysis
							

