All adverse events that occur after the consent form is signed but before treatment allocation/randomization must be reported by the investigator if they cause the subject to be excluded from the trial, or are the result of a protocol-specified intervention, including but not limited to washout or discontinuation of usual therapy, diet, placebo treatment or a procedure. From the time of treatment allocation/randomization through 14 days following cessation of treatment, all adverse events must be reported by the investigator. Such events will be recorded at each examination on the Adverse Event case report forms/worksheets. The reporting timeframe for adverse events meeting any serious criteria is described in section 7.2.3.1. The investigator will make every attempt to follow all subjects with non-serious adverse events for outcome.

Electronic reporting procedures can be found in the Electronic Data Capture (EDC) data entry guidelines. Paper reporting procedures can be found in the Investigator Trial File Binder (or equivalent).

7.2.1 Definition of an Overdose for This Protocol and Reporting of Overdose to the Sponsor

In this trial, an overdose in IV study therapy is defined as administration of a total daily dose of IMI/REL in excess of 4 g (IMI) or 2 g (REL).

If an adverse event(s) is associated with ("results from") the overdose of Sponsor's product or vaccine, the adverse event(s) is reported as a serious adverse event, even if no other seriousness criteria are met.

If a dose of Sponsor's product or vaccine meeting the protocol definition of overdose is taken without any associated clinical symptoms or abnormal laboratory results, the overdose is reported as a non-serious Event of Clinical Interest (ECI), using the terminology "accidental or intentional overdose without adverse effect."

All reports of overdose with and without an adverse event must be reported by the investigator within 24 hours to the Sponsor either by electronic media or paper. Electronic

reporting procedures can be found in the EDC data entry guidelines. Paper reporting procedures can be found in the Investigator Trial File Binder (or equivalent).

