7.2.3 Immediate Reporting of Adverse Events to the Sponsor

7.2.3.1 Serious Adverse Events

A serious adverse event is any adverse event occurring at any dose or during any use of Sponsor's product that:

- Results in death;
- Is life threatening;
- Results in persistent or significant disability/incapacity;
- Results in or prolongs an existing inpatient hospitalization;
- Is a congenital anomaly/birth defect;
- Is an other important medical event.

Note: In addition to the above criteria, adverse events meeting either of the below criteria, although not serious per ICH definition, are reportable to the Sponsor in the same timeframe as SAEs to meet certain local requirements. Therefore, these events are considered serious by the Sponsor for collection purposes.

- Is a cancer;
- Is associated with an overdose.

Refer to [Table 16](#) for additional details regarding each of the above criteria.

For the time period beginning when the consent form is signed until treatment allocation/randomization, any serious adverse event, or follow up to a serious adverse event, including death due to any cause, that occurs to any subject must be reported within 24 hours to the Sponsor if it causes the subject to be excluded from the trial, or is the result of a protocol-specified intervention, including but not limited to washout or discontinuation of usual therapy, diet, placebo treatment or a procedure.

For the time period beginning at treatment allocation/randomization through 14 days following cessation of treatment, any serious adverse event, or follow up to a serious adverse event, including death due to any cause, whether or not related to the Sponsor's product, must be reported within 24 hours to the Sponsor either by electronic media or paper. Electronic reporting procedures can be found in the EDC data entry guidelines. Paper reporting procedures can be found in the Investigator Trial File Binder (or equivalent).

Additionally, any serious adverse event, considered by an investigator who is a qualified physician to be related to the Sponsor's product that is brought to the attention of the investigator at any time outside of the time period specified in the previous paragraph also must be reported immediately to the Sponsor.

All subjects with serious adverse events must be followed up for outcome.

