7.2.3.2 Events of Clinical Interest

Selected non-serious and serious adverse events are also known as Events of Clinical Interest (ECI) and must be reported to the Sponsor.

For the time period beginning when the consent form is signed until treatment allocation/randomization, any ECI, or follow up to an ECI, that occurs to any subject must be reported within 24 hours to the Sponsor if it causes the subject to be excluded from the trial, or is the result of a protocol-specified intervention, including but not limited to washout or discontinuation of usual therapy, diet, placebo treatment or a procedure.

For the time period beginning at treatment allocation/randomization through 14 days following cessation of treatment, any ECI, or follow up to an ECI, whether or not related to the Sponsor's product, must be reported within 24 hours to the Sponsor, either by electronic media or paper. Electronic reporting procedures can be found in the EDC data entry guidelines. Paper reporting procedures can be found in the Investigator Trial File Binder (or equivalent).

Events of clinical interest for this trial include:

1. an overdose of Sponsor's product, as defined in Section 7.2.1 - Definition of an Overdose for This Protocol and Reporting of Overdose to the Sponsor, that is not associated with clinical symptoms or abnormal laboratory results.
2. an elevated AST or ALT lab value that is greater than or equal to 3X the upper limit of normal and an elevated total bilirubin lab value that is greater than or equal to 2X the upper limit of normal and, at the same time, an alkaline phosphatase lab value that is less than 2X the upper limit of normal, as determined by way of protocol-specified laboratory testing or unscheduled laboratory testing.*

*Note: These criteria are based upon available regulatory guidance documents. The purpose of the criteria is to specify a threshold of abnormal hepatic tests that may require an additional evaluation for an underlying etiology. The trial site guidance for assessment and follow up of these criteria can be found in the Investigator Trial File Binder (or equivalent).

3. a confirmed (i.e., verified by repeat testing) elevated AST or ALT laboratory value that is greater than or equal to 5 X ULN as a result of within-protocol-specific testing or unscheduled testing.

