9.0 LABELING, PACKAGING, STORAGE AND RETURN OF CLINICAL SUPPLIES

9.1 Investigational Product

The investigator shall take responsibility for and shall take all steps to maintain appropriate records and ensure appropriate supply, storage, handling, distribution and usage of investigational product in accordance with the protocol and any applicable laws and regulations.

Clinical Supplies will be provided by the Sponsor as summarized in [Table 20](#).

Clinical supplies will be packaged to support enrollment and replacement subjects as required. When a replacement subject is required, the Sponsor or designee needs to be contacted prior to dosing the replacement supplies.

Table 20 Product Descriptions

Product Name & Potency	Dosage Form	Source/Additional Information
MK-7655A, MK-7655 250 mg /Imipenem 500 mg / Cilastatin 500 mg	Powder for Constitution	Provided centrally by the Sponsor

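### The fixed daily overdose limit in Section 7.2.1 ignores the renal dose bands, so at CrCl 15 to <30 a whole vial every 6 hours (2.5 times the assigned dose) needs no overdose report; a small safety-reporting improvement

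*Combined protocol and SAP*

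**What the plan says.** - **Definition.** Section 7.2.1 sets the limit as "administration of a total daily dose of IMI/REL in excess of 4 g (IMI) or 2 g (REL"). It mentions neither renal function nor the assigned dose. The documents do not say how the figures were chosen.
- **Dosing.** Section 5.2.1.1 says that "the dose must be adjusted based upon the degree of renal function impairment". Table 13 assigns 500/250, 400/200, 300/150 and 200/100 mg IMI/REL at CrCl ≥90, 60 to <90, 30 to <60 and 15 to <30 mL/min. Section 5.2.2 keeps the interval at 6 hours in every band. Flow chart footnote 4 adds: "The most recently collected creatinine clearance should be used to support dosage determination".
- **Supply.** Table 20 lists one product strength, "MK-7655A, MK-7655 250 mg /Imipenem 500 mg / Cilastatin 500 mg". Table 13 footnote a says "IMI/REL is provided as a single vial in a fixed-dose combination; therefore, the dose for each component will be adjusted equally during preparation".
- **Consequences.** Under Section 7.2.1 any overdose goes to the sponsor within 24 hours. If an adverse event results from it, "the adverse event(s) is reported as a serious adverse event, even if no other seriousness criteria are met". Section 7.2.3.1 describes such events as "although not serious per ICH definition, are reportable to the Sponsor in the same timeframe as SAEs to meet certain local requirements". Item 1 of Section 7.2.3.2 makes an overdose as defined in 7.2.1 an event of clinical interest (ECI) if it is one "that is not associated with clinical symptoms or abnormal laboratory results".

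**The concern.** The dose is scaled to renal function; the overdose limit is not. Section 4.1.2 reports that relebactam, imipenem and cilastatin are cleared almost entirely by the kidney in healthy subjects, that renal impairment markedly altered clearance and AUC, and that relebactam exposure rises in proportion to dose. A given excess therefore matters most in the band where the limit is loosest relative to the assigned dose.

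That band is part of the trial: Section 5.1.3 excludes only CrCl below 15, and Section 8.10 plans a subgroup below 30. A natural error there is to give the whole vial where a part is due, or to continue 500/250 mg after renal function has fallen.

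Two reports are at stake. An event-free whole-vial day would not be an ECI and would need no 24-hour report. A non-serious adverse event resulting from it would not be handled as serious on account of overdose.

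**Working it through.** **Inputs.** Limit 4 g IMI / 2 g REL per day (7.2.1); dose per infusion (Table 13); four infusions a day (5.2.2); vial 500/250 mg (Table 20). IMI and REL are always given 2:1, so the ratios are the same for both; IMI is shown.

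**Where the limit sits.** Full daily dose = 4 × 500 mg = 2.0 g, and 4.0 / 2.0 = 2.0. The limit is exactly twice the full daily dose, although the protocol does not give that as its basis.

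**By band.** Assigned daily dose = 4 × Table 13 dose. Whole vial every 6 hours = 4 × 500 mg = 2.0 g.

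| CrCl (mL/min) | Assigned per day | Limit / assigned | Whole vials / assigned | Overdose now? |
|---|---|---|---|---|
| ≥90 | 2.0 g | 2.0 | 1.0 | No (correct dose) |
| 60 to <90 | 1.6 g | 2.5 | 1.25 | No |
| 30 to <60 | 1.2 g | 3.33 | 1.67 | No |
| 15 to <30 | 0.8 g | 5.0 | 2.5 | No |

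Only in the lowest band does the whole-vial error exceed twice the assigned dose, and there it is 2.0 / 4.0 = 50% of the limit.

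**Limits with the same factor of 2 in each band.** 2 × assigned = 4.0, 3.2, 2.4 and 1.6 g IMI (2.0, 1.6, 1.2 and 0.8 g REL). Whole vials needed in a day to exceed them: 9, 7, 5 and 4, against 9 in every band now.

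**What this would flag.** An all-day error with too high a Table 13 strength can take six forms, with these ratios given/assigned: 500/400 = 1.25; 400/300 = 1.33; 300/200 = 1.5; 500/300 = 1.67; 400/200 = 2.0 (not above 2); 500/200 = 2.5 (flagged). In the lowest band with four infusions, 1, 2, 3 or 4 whole vials and the rest correct give 1.1, 1.4, 1.7 or 2.0 g, so three or four exceed 1.6 g.

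**Compliant days.** If D is the highest dose assigned that day, four correct infusions total at most 4D against a limit of 8D, that is, at most half. For example, 500 + 500 + 500 + 200 mg = 1.7 g against 4.0 g. If the 60-minute administration window in 5.2.2 put five infusions into one day, the total would be at most 5/8 = 62.5% of the limit.

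**Frequency (assumed).** The documents give neither the share of subjects at CrCl 15 to <30 nor an error rate. Assume 2% to 15% of the 80 subjects in that band, and a whole-vial day in 1% to 10% of those:

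- low: 80 × 0.02 × 0.01 = 0.016 subjects; chance of at least one = 1 − (1 − 0.0002)^80 = 1.6%
- high: 80 × 0.15 × 0.10 = 1.2 subjects; chance of at least one = 1 − (1 − 0.015)^80 = 70%

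**The case against.** A fixed reporting limit is a legitimate choice, and Sections 7.2.3.1, 7.2.3.2 and Table 16 use the overdose concept without contradiction. Other safeguards bear on the error:

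- dose adjustment is mandatory and renal function is monitored (5.2.1.1);
- administration is witnessed (7.1.1.9);
- creatinine values that set or change the dose are entered in the eCRF (7.1.3.1);
- the sponsor verifies data against source (12.1);
- a subject may be taken off treatment for a violation of the trial plan (5.8.1);
- exposure is evaluated (8.12);
- Table 16 lets medical judgement make an adverse event serious as an important medical event.

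The rationale for the limit and further preparation checks may lie in the Investigator's Brochure or the Pharmacy Manual, which are not available here. The frequency range is too wide to show a practical need, and the factor 2 is not in the protocol.

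Most of this stands, and it is why the point is minor: the documents show a gap, not an error. But the safeguards make the mistake less likely or easier to find later; none requires the overdose report. Section 7.1.1.8 requires consultation for interruptions only, and Section 8.11 counts doses, so four whole vials out of four expected infusions score 100% compliance.

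A reader might infer that the protocol tolerates five times the intended dose, or that excess dosing in renal impairment escapes safety follow-up. The documents support neither. Five is the ratio at the limit, not an expected error, and Table 13 is binding whatever counts as an overdose. All adverse events through 14 days after treatment, events serious on other grounds, and the two liver ECIs are still reported.

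**Conclusion.** The gap is real and small. In the lowest renal band, 2.5 times the assigned daily dose is not an overdose, whereas at normal renal function anything above 2 times is. The loss is confined to the overdose ECI with its 24-hour report and to the overdose-based serious handling of a resulting non-serious adverse event. In the mild and moderate bands the whole-vial error is 1.25 and 1.67 times the assigned dose, below the ratio that the protocol accepts at full dose, so the point does not extend to them. Efficacy and sample size are not affected.

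The ratios rest on document figures alone. The number of subjects affected rests on assumption (0.016 to 1.2) and may be near zero. This is a cheap improvement, not a correction that the trial's conclusions depend on.

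**What to change.** In Section 7.2.1, define overdose as a total daily dose of more than 2 times the full-day (four-infusion) Table 13 dose for the highest dose band assigned on that day, based on the CrCl result available to the site when each dose was prepared. From the highest to the lowest band the limits are >4.0/2.0, >3.2/1.6, >2.4/1.2 and >1.6/0.8 g IMI/REL.

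Two features matter:

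- **No scaling to the infusions given.** A scaled limit would flag one whole vial on a one-infusion day in the lowest band (0.5 g against 2 × 0.2 = 0.4 g) but not two whole vials plus two correct doses on a full day (1.4 g against 1.6 g). With a full-day limit, a larger total in the same band is never treated more leniently than a smaller one.
- **The result available at preparation.** Section 7.1.3.1 warns that central laboratory results will probably come too late for patient management. Dosing in good faith should not become an overdose when a later result arrives.

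The cost is a change to one definition; item 1 of Section 7.2.3.2 already refers back to it. The full-dose limit stays as it is and compliant dosing is not flagged. Expect a few more 24-hour reports, mainly in the lowest band.

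Some errors remain unflagged: 400/200 mg given for 200/100 mg all day (exactly 2 times); partial days, for example three whole vials on a three-infusion day (1.5 g against 1.6 g); and 500/250 mg wrongly continued on the day CrCl falls into the lowest band. In the last case the next full day is flagged (2.0 g against 1.6 g). The factor 2 is a proposal that carries over the existing full-dose ratio; any factor below 2.5 would catch four whole vials in the lowest band.

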7.2.2 Reporting of Pregnancy and Lactation to the Sponsor

Although pregnancy and lactation are not considered adverse events, it is the responsibility of investigators or their designees to report any pregnancy or lactation in a subject (spontaneously reported to them) that occurs during the trial.

Pregnancies and lactations that occur after the consent form is signed but before treatment allocation/randomization must be reported by the investigator if they cause the subject to be excluded from the trial, or are the result of a protocol-specified intervention, including but not limited to washout or discontinuation of usual therapy, diet, placebo treatment or a procedure. Pregnancies and lactations that occur from the time of treatment allocation/randomization through 14 days following cessation of Sponsor's product must be reported by the investigator. All reported pregnancies must be followed to the completion/termination of the pregnancy. Pregnancy outcomes of spontaneous abortion, missed abortion, benign hydatidiform mole, blighted ovum, fetal death, intrauterine death, miscarriage and stillbirth must be reported as serious events (Important Medical Events). If the pregnancy continues to term, the outcome (health of infant) must also be reported.

Such events must be reported within 24 hours to the Sponsor either by electronic media or paper. Electronic reporting procedures can be found in the EDC data entry guidelines. Paper reporting procedures can be found in the Investigator Trial File Binder (or equivalent).

